#### 7.4.2.6. Prompt Reporting of SAEs and Other Events to GSK

SAEs and pregnancies must be reported promptly by the investigator to GSK as described in the following table once the investigator determines the event meets the protocol definition for that event.

Initial Reports		Initial Reports		formation on a s Report
Type of Event	Time Frame	Documents	Time Frame	Documents
All SAEs	24 hours	SAE CRF	24 hours	Updated SAE CRF
Pregnancy	2 Weeks	Pregnancy Notification Form	2 Weeks	Pregnancy Follow up Form

Methods for detecting, recording, evaluating, and following up on AEs and SAEs are provided in the SPM.

#### 7.4.2.7. Regulatory reporting requirements for SAEs

Prompt notification of SAEs by the investigator to GSK is essential so that legal obligations and ethical responsibilities towards the safety of patients are met.

GSK has a legal responsibility to notify both the local regulatory authority and other regulatory agencies about the safety of a product under clinical investigation. GSK will comply with country specific regulatory requirements relating to safety reporting to the regulatory authority, Institutional Review Board (IRB)/Independent Ethics Committee (IEC) and investigators.

Investigator safety reports are prepared for suspected unexpected serious adverse reactions according to local regulatory requirements and GSK policy and are forwarded to investigators as necessary.

An investigator who receives an investigator safety report describing a SAE(s) or other specific safety information (e.g., summary or listing of SAEs) from GSK will notify the IRB/IEC, if appropriate according to local requirements.

# 7.4.3. Pregnancy Reporting

Any pregnancy that occurs during study participation must be reported using a pregnancy form. To ensure patient safety, each pregnancy must be reported to GSK within 2 weeks of learning of its occurrence. The pregnancy must be followed up to determine outcome (including premature termination) and status of mother and child. Pregnancy complications and elective terminations for medical reasons must be reported as an AE or SAE. Spontaneous abortions must be reported as an SAE.

Any SAE occurring in association with a pregnancy brought to the investigator's attention after the patient has completed the study and considered by the investigator as possibly related to the study treatment, must be promptly reported to GSK.

In addition, the investigator must attempt to collect pregnancy information on any female partners of male study patients who become pregnant while the patient is enrolled in the study. Pregnancy information must be reported to GSK as described above.

## 7.4.4. Laboratory Assessments

Table 2 Laboratory Assessments (if performed)

Hematology	Standard Chemistry	Other
Hemoglobin*	Sodium	C-reactive protein (CRP)
Hematocrit	Potassium	Thyroid-stimulating hormone (TSH) or thyrotropin
Platelet count*	Calcium*	
Absolute neutrophil count*	Phosphate	
	Blood urea nitrogen or urea	
	Creatinine	
	Lactate dehydrogenase (LDH)*	
	Aspartate aminotransferase (AST)	
	Alanine aminotransferase (ALT)	
	Total bilirubin	
	Total protein	
	Albumin	_

\*These values, particularly at baseline, are critical for evaluation of patient risk category at enrollment

#### 7.5. Health Outcomes

# 7.5.1. Health Outcomes Endpoints

Health-related quality of life (HRQoL) will be assessed using the EQ-5D (3L) Index and VAS, the FKSI-19 and the FACIT Fatigue scale. These assessments will be restricted to sites where the administration of HRQoL questionnaires is permitted and has received local ethical and/or regulatory approval.

## 7.5.2. Health Outcomes Assessments

The Euro Qol (EQ-5D 3L) questionnaire is a generic preference-based QoL measure comprised of a 5-item health status measure and a visual analogue scale (VAS) [Kind, 1996; Rabin, 2001] and used to generate two scores. The EQ-5D utility score is based on answers to 5 questions that evaluate mobility, self-care, usual activities, pain, discomfort, and anxiety and/or depression. Answers range from 1 to 3, depending on whether the patients perceives no problems (= 1), some problems (= 2), or significant problems (= 3) in that aspect of their health. The EQ-5D VAS generates a single health status index in which patients are asked to rate their current health by drawing a line from a box marked,

"Your health state today" to the appropriate point on a 20-cm visual analog scale ranging from 100 (best imaginable health state) to 0 (worst imaginable health state). Patients will complete the EQ-5D at baseline and approximately every 3 months thereafter.

The Functional Assessment of Cancer Therapy-Kidney Symptom Index-19 (FKSI-19) measures disease and treatment-related symptoms specifically in renal cancer patients. FKSI-19 uses five point Likert scale ranging from 'not at all' (0) to 'very much' (4). It includes patients self-reports on experience of symptoms in the past seven days such as lack of energy, pain, bone-pain, shortness of breath, fatigue and blood in urine [Cella, 2006]. Patients will complete the FKSI-19 at baseline and approximately every 3 months thereafter.

The Functional Assessment of Chronic Illness Therapy (FACIT) Fatigue scale is a short, 13-item validated instruments that measures a patient's level of fatigue during the usual activities over the past 7 days, based on a four point Likert scale ranging from 'not at all fatigued' (4) to 'very much fatigued' (0) [Webster, 2003]. Patients will complete the FACIT Fatigue scale at baseline and approximately every 3 months thereafter.

#### 8. DATA MANAGEMENT

Patient data will be collected using defined electronic case report forms (eCRFs), transmitted electronically to GSK and combined with data provided from other sources in a validated data system.

All data will be collected and entered by the participating sites directly into the EDC system. All sites will be fully trained for using the on-line data capture system, including eCRF completion guidelines and help files. Sites will have the ability to add a new record, to search for and modify existing records, to search for patients for whom followup is due, to identify records with outstanding queries and to identify records that require signatures. Throughout participation in the study, individual physicians will have access to their own patients' data and select reports via the EDC system. The study database will be housed in a physically and logically secure computer system maintained in accordance with a written security policy. The system meets approved established standards for the security of health information and is validated. The system also meets the standards of the International Committee on Harmonisation (ICH) guideline E6R1 regarding electronic study data handling. Patient confidentiality will be strictly maintained. Data quality will be confirmed through a series of programmed data quality checks that automatically detect out-of-range or anomalous data, as detailed in the study data monitoring plan. A clinical monitoring plan, including for-cause monitoring, that is appropriate for the study design will also be developed and implemented.

Management of clinical data will be performed in accordance with applicable GSK standards and data cleaning procedures to ensure the integrity of the data, e.g., removing errors and inconsistencies in the data. Adverse events terms will be coded using MedDRA eCRFs (including queries and audit trails) will be retained by GSK, and copies will be sent to the investigator to maintain as the investigator copy.

In all cases, patient initials will not be collected or transmitted to GSK according to GSK policy.

2011N118677\_00 **CONFIDENTIAL** VEG115232

## 9. DATA ANALYSIS AND STATISTICAL CONSIDERATIONS

# 9.1. Study Design Considerations

### 9.1.1. Sample Size Assumptions

Due to the descriptive nature of the study, no formal sample size estimation was conducted. The targeted sample size was based on the expected precision around the estimates for the outcomes of interest, and the feasibility of enrolling the desired population during the enrolment period. Since consecutive enrollment of eligible patients is sought, it is unknown what the distribution of patient baseline characteristics will be and the sample size does not take into consideration subgroup size (e.g., the number of elderly patients enrolled). No formal hypothesis or statistical significance testing is planned. This approach follows the *Guidelines for Good Pharmacoepidemiology Practices*, Section D, point 10.

Recent clinical trial data were reviewed in order to identify applicable rates to apply to sample size estimations, to determine the number of patients needed.

#### **Progression-Free Survival**

In VEG105192, the PFS rate at 12 months (estimated from the Kaplan-Meier estimate) was approximately 45% [Sternberg, 2010]. Taking this as a baseline proportion, the sample sizes (N) required for different levels of precision are shown in Table 3. These are calculated using the normal approximation to the binomial proportion distribution.

Table 3	Sample size estimates	for PFS (at 12 months	post-enrollment)
---------	-----------------------	-----------------------	------------------

Precision (half-width)	10%	5%	4%	3%
Estimated 95% CI	(35%, 55%)	(40%, 50%)	(41%, 49%)	(42%, 48%)
N	96	381	595	1057

A sample size of 700 patients will provide for a precision of less than 4% for PFS at 12 months.

#### **Overall Response Rate (ORR)**

In the phase III registration study of pazopanib (VEG105192), the overall response rate (ORR) observed in the pazopanib arm was 30% [Sternberg, 2010]. Using this as a baseline proportion, the sample sizes (N) required for several different levels of precision are shown in Table 4. These are calculated using the normal approximation to the binomial proportion distribution.

Precision (half-width)	10%	5%	4%	3%
Estimated 95% CI	(20%, 40%)	(25%, 35%)	(26%, 34%)	(27%, 33%)
N	81	323	505	897

A sample size of 700 patients will provide for a precision of less than 4% for OSS at 12 months

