# 4. PATIENT SELECTION AND DISCONTINUATION/COMPLETION CRITERIA

#### 4.1. Patient Selection Criteria

#### 4.1.1. Number of Patients

Approximately 700-1000 patients will be enrolled. See Section 9.1.1 for sample size assumptions.

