#### 9.2.2. Treatment Comparisons

#### 9.2.2.1. Primary Comparisons of Interest

As this is a single arm study, there are no treatment comparisons. Effectiveness (OS and PFS), safety and health outcome endpoints will be summarized utilizing the AT population. Evaluation of overall response rates will be restricted to those patients with measurable disease at baseline (i.e., the MD population).

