#### 9.2.4.1. Effectiveness Analyses

## 9.2.4.1.1. Primary Analysis

The primary analysis will evaluate the [population on OS and PFS based on the investigator's assessment, as defined in Section 7.3. Censoring rules will be outlined in detail in the RAP. PFS and OS duration will be summarised using Kaplan-Meier methods. Rates of PFS and OS at 12 months will be summarised. AT will be the primary population.

The overall response rate (ORR) will be based on the investigator assessment of overall response in the MD population. Patients with unknown or missing response will be treated as non-responders, i.e. they will be included in the denominator when calculating the percentage. Separate summaries of the number and percentage of patients with only non-measurable disease who achieve a best response of CR or SD will be provided. Exact methods for calculated confidence intervals will be utilized.

Several sensitivity analyses will be conducted in order to confirm the results of the primary analysis. Some key sensitivity analyses are provided below. Additional sensitivity analyses will be defined in the RAP.

- 1. The first sensitivity analysis, limited to the MD population, will be based on investigators' assessment of progression together with clinical evidence of symptomatic deterioration determined by investigator. This analysis will take into account the fact that some patients may have progression based on clinical evidence of symptomatic deterioration prior to documentation of progression via CT/MRI.
- 2. The second sensitivity analysis will be based on the patients in the MD population for whom follow-up was conducted consistent with RECIST 1.1.
- 3. The third sensitivity analysis will take into account the extended lost-to-follow up. If a progression event occurs after an extended lost-to-follow-up time the primary analysis will censor those patients at the date of their last visit with an adequate assessment even if subsequent information is available regarding tumour measurements or date of death. The extended lost-to-follow-up will be defined in the RAP.
- 4. The fourth sensitivity analysis will assign the start date of the new anti-cancer therapy as the progression date for patients who start a new anti-cancer therapy without documented disease progression in the primary analysis.

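### The ORR precision statement is computed on all 700 patients and mislabelled, while ORR is analysed only in patients with measurable disease, whose number the protocol never states

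*Protocol*

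**What the plan says.** Section 9.1.1 says that no formal sample size estimation was done and that the target rests on expected precision and on feasibility of enrolment. For ORR it takes its base rate from the phase III registration study, where "the overall response rate (ORR) observed in the pazopanib arm was 30" per cent. It tabulates the N needed for several half-widths by the normal approximation, then concludes: "A sample size of 700 patients will provide for a precision of less than 4% for OSS at 12 months".

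The analysis sections define the ORR denominator differently. Section 9.2.2.1 states: "Evaluation of overall response rates will be restricted to those patients with measurable disease at baseline (i.e., the MD population". Section 9.2.1 names this the primary population for ORR, and Section 9.2.4.1.1 repeats it. That section adds, for the intervals: "Exact methods for calculated confidence intervals will be utilized". Patients with unknown or missing response stay in the denominator as non-responders.

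Sections 4.1.2 and 4.1.3 do not require measurable disease. Section 7.1.1 only records it as yes or no. On enrolment, Section 4.1.1 says: "Approximately 700-1000 patients will be enrolled".

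**The concern.** Two things do not fit. First, the sentence names an endpoint and a time point that do not belong to the calculation. Its section heading, base rate and table are all for ORR, and Sections 2 and 7.3.1 define ORR as a documented response at any time.

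Second, the sentence puts 700 in the denominator, whereas ORR will be estimated in MD patients only. Section 9.2.4.1.1 plans separate summaries for patients with only non-measurable disease, so the protocol itself expects the MD population to be smaller than the whole. It gives no figure for how much smaller.

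The study is descriptive, and Section 9.2.4 bases interpretation on point estimates and 95% confidence intervals. Expected precision is therefore the main quantitative support for the target of 700. For a primary effectiveness measure, the printed figure describes a denominator that the analysis will not use.

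**Working it through.** **Inputs.** Response rate p = 0.30, a two-sided 95% interval (z = 1.96), the normal approximation and N = 700 come from the ORR paragraph of Section 9.1.1. The MD denominator comes from Sections 9.2.1 and 9.2.2.1, and the exact interval from Section 9.2.4.1.1. The MD shares below are assumptions, because the protocol gives none.

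**Step 1: reproduce the protocol's table.** N = z² p(1 − p) / h², with p(1 − p) = 0.21.

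| Half-width h | Computed N | Rounded up | Protocol |
|---|---|---|---|
| 10% | 80.67 | 81 | 81 |
| 5% | 322.68 | 323 | 323 |
| 4% | 504.19 | 505 | 505 |
| 3% | 896.34 | 897 | 897 |

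All four entries agree.

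**Step 2: half-width at 700.** 1.96 × √(0.21/700) = 3.39 points. The exact (Clopper-Pearson) interval has a half-width of 3.46 points, taken as half its total length. Both are below 4, so the statement is correct if all 700 patients are in the denominator.

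**Step 3: break-even MD size.** By the protocol's formula, 505 MD patients are needed: 505/700 = 72.1%. With the exact interval, the smallest size that gives less than 4 points is about 527: 527/700 = 75.3%.

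**Step 4: half-width by assumed MD share of 700.**

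| MD share | MD patients | Normal approximation (points) | Exact (points) |
|---|---|---|---|
| 100% | 700 | 3.39 | 3.46 |
| 90% | 630 | 3.58 | 3.65 |
| 80% | 560 | 3.80 | 3.88 |
| 75% | 525 | 3.92 | 4.01 |
| 70% | 490 | 4.06 | 4.15 |
| 60% | 420 | 4.38 | 4.49 |

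Missing responses do not reduce these sizes further, because they count as non-responders.

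**Step 5: upper end of enrolment.** With 1000 patients the same break-even sizes are 505/1000 = 50.5% (normal) and 527/1000 = 52.7% (exact).

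**Step 6: the PFS statement, for comparison.** The protocol reports that "the PFS rate at 12 months (estimated from the Kaplan-Meier estimate) was approximately 45" per cent, and concludes: "A sample size of 700 patients will provide for a precision of less than 4% for PFS at 12 months". At 700 fully observed patients the half-width is 1.96 × √(0.45 × 0.55/700) = 3.69 points. It reaches 4.00 at an effective 595, and 1 − 595/700 = 15% loss of information. If PFS and independent censoring are both assumed exponential, that corresponds to about 17% of patients censored before 12 months.

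**The case against.** The strongest reply is that nothing has been computed wrongly. Every tabulated N reproduces, and the half-width at 700 is comfortably below 4. The protocol contains no MD share that would break the claim. About 28% of 700 could lack measurable disease before the normal-approximation figure passes 4 points, or about 25% with the exact interval. Moreover, 700 is the lower end of the enrolment range, and Section 9.1.2 allows recruitment to be revised. The study plans no hypothesis test on ORR, and going from 4.0 to 4.5 points would change no decision. A reader can also find approximate precision for a smaller group in the ORR table, which is indexed by N.

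Most of this stands. It rules out reading the point as an arithmetic error or as proof that 700 is too few. It does not remove the mismatch, because the sentence itself names 700 and not a larger number.

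Section 9.1.1 does say that the distribution of baseline characteristics is unknown and that subgroup size was not considered. But MD is the primary ORR population, not a subgroup. The same section gives RDI precision at 420 and 490 patients for a secondary population, so a similar statement for ORR would be in keeping with it.

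Three stronger readings are tempting, and the documents do not support them:

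- **That the PFS statement is also wrong because PFS will be censored.** The protocol labels its calculation as a binomial approximation. It plans 30 months of follow-up, including after treatment stops, and counts clinical deterioration as progression. It states no censoring rate. The absence of censoring before 12 months is a caveat to that figure, not an error in it.
- **That planning by normal approximation and analysing by exact methods is a contradiction.** The difference is 0.07 points at 700 and 0.09 at 490.
- **That the odd label hides a precision claim for overall survival with no calculation behind it.** The heading, base rate and table all identify ORR, so this is a labelling slip.

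**Conclusion.** The point holds in a limited form. The ORR precision sentence names the wrong endpoint and time point, and it rests on a denominator that the planned ORR analysis does not use. The claim of less than 4 points is correct for 700 patients. For the planned analysis it depends on at least 505 MD patients by the protocol's formula, or about 527 with the exact interval, and the protocol states neither condition.

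A reader might infer that the study will miss its ORR precision or needs more patients. The documents do not show that. The failing cases rest on assumed MD shares below about 75% of 700. Over the range shown, the half-width is at most 4.49 points, and enrolment towards 1000 would restore the claim down to an MD share of roughly one half. All figures assume a 30% response rate. This is a low-cost correction to a stated justification. It does not challenge the design.

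**What to change.** In the ORR paragraph of Section 9.1.1, replace the endpoint label with ORR in the MD population and delete the reference to 12 months. Then do one of the following:

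- give the exact 95% half-width at a 30% response rate for assumed MD sizes: 420 patients, 4.49 points; 490, 4.15; 560, 3.88; 630, 3.65. Say that the sizes are assumptions; or
- keep the claim of less than 4 points and state that it requires at least about 527 MD patients.

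Optionally, add to the PFS paragraph that its figure (3.69 points at 700) assumes no censoring before 12 months and reaches 4.00 at an effective 595.

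The cost is one reworded sentence and a short table or a condition. No patients, data items or analyses change. The quoted ORR precision becomes slightly less favourable, but it then describes the analysis that will be done.

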# **Relative Dose Intensity (RDI)**

Relative dose intensity (RDI) will be evaluated using a one sample t-test to compare the RDI against an estimate obtained from the Phase III registration study for pazopanib [VEG105192] using a minimal acceptable value (the average RDI obtained from the VEG105192 minus a margin of inferiority of 0.1).

The sample size is determined by the formula:  $N = (Z_{1-\alpha/2} + Z_{1-\beta})^2 * \sigma^2 / \delta^2$ 

Where  $\sigma$  is the estimated standard deviation for the RDI distribution and  $\delta$  is the difference to be detected. An  $\alpha$  (type I error) of 0.05 and  $\beta$  (type II error) of 0.10 is assumed (for 90% power).

If the mean RDI in this observational study is assumed to be the same as in VEG105192,  $\delta$  would be equivalent to the inferiority margin. However, the expected RDI in the real world setting should conceivably be slightly smaller than the RDI in the clinical trial setting, therefore for the purposes of sample size estimation a 0.05 decrement was used (i.e.,  $\delta$  = inferiority margin – 0.05).

A reasonable assumption for the standard deviation would be 0.25. The standard deviation calculated from VEG105192 was 0.185, and a larger standard deviation might be expected for an observational study. Table 4 gives the number of patients required to obtain the specified precision, assuming a standard deviation (SD) of 0.25 and a more conservative value of 0.4. Within the table, the precision is related to the SD by the formula: precision = Z[1 - alpha/2] \* SD/sqrt(N)

Table 4 Sample size estimates for RDI

Precision (half-width)	0.1	0.1	0.05	0.05	0.03	0.03
Estimated 95% C.I.	(0.775, 0.975)		(0.825, 0.925)		(0.845, 0.905)	
Std. Dev.	0.25	0.4	0.25	0.4	0.25	0.4
N	25	62	97	246	267	683

Based on the results from the sample size estimations, it can be seen that a total of 700 is sufficient to generate a power of 90% even in pessimistic assumptions (small margin of inferiority, large standard deviation for RDI and average RDI for real-world setting somewhat lower than in VEG105192).

Secondary analyses will be carried out on the subgroup of patients who would have been eligible for VEG105192 ("clinical trial eligible" subgroup). Assuming that 60 or 70% of patients in the observational study (i.e., between 420 and 490 of the enrolled patients) will be considered clinical trial eligible, the precision for RDI will be as follows for different values of the standard deviation is shown in Table 5.

N 420 420 420 490 490 490 Std. Dev. 0.25 0.30 0.40 0.25 0.30 0.40 Precision (half-0.024 0.029 0.038 0.022 0.027 0.035

Table 5 Sample size estimates for RDI (clinical trial eligible)

